6.1 Description of the Investigational Device

698

6.1.1 Insulin Pump

699

The study system will include the Tandem t:slim X2 with Control-IQ Technology.

700

6.1.2 Continuous Glucose Monitoring

701

The study CGM will include Dexcom G6 transmitter and sensors when using the Tandem t:slim X2 with Control-IQ technology. The CGM sensor will be replaced at least once every 10 days.

703

6.1.3 Blood Glucose Meter and Strips

704

Blood glucose levels will be measured using the study's blood glucose meter (glucometer) and the CGM device will be calibrated if needed using the study glucometer and strips in accordance with the manufacturer's labeling.

707

6.1.3.1 Blood Glucose Meter Testing

708

- All study blood glucose meters will be QC tested with at least two different concentrations of control solution if available during all office visits. A tested meter will not be used in a study if it does not read within the target range at each concentration per manufacturer labeling.
- Participants will be reminded to use the study blood glucose meter for all fingerstick blood glucose measurements.

713

6.1.3.2 Blood Glucose Meter Supplies

714

- Participants will be provided all necessary supplies during the study.
- Participants will be permitted to keep these devices at the conclusion of the study.

716

6.1.4 Blood Ketone Meter and Strips

717

Blood ketone levels will be measured using the Abbott Precision Xtra Ketone Meter and strips in accordance with the manufacturer's labeling. The blood glucose meter component of the Precision Xtra device will not be used.

720

6.1.4.1 Blood Ketone Testing

721

- All study blood ketone meters will be QC tested with at least two different concentrations of control solution if available during all office visits. A tested meter will not be used in a study if it does not read within the target range at each concentration per manufacturer labeling.
- Participants will be instructed on how to perform blood ketone testing.
- Participants will be given guidelines for treatment of elevated blood ketones.

726

6.1.4.2 Blood Ketone Meter Supplies

727

- Participants will be provided all necessary supplies during the study.
- Participants will be permitted to keep these devices at the conclusion of the study.

729 **6.1.5 Activity Tracker**

730 • Participants will be trained on the study activity tracker that will be used to collect additional
731 information about movement and heart rate.

732 • Participants will be asked to wear the device during the entire study. The monitor can be
733 removed during bathing.

734 **6.1.6 Study Device Accountability Procedures**

735 Device accountability procedures will be detailed in the site procedures manual.

736 **6.1.7 Blood Ketone Testing**

737 • All study blood ketone meters will be QC tested with at least two different concentrations of
738 control solution if available during all office visits. A tested meter will not be used in a study
739 if it does not read within the target range at each concentration per manufacturer labeling.

740 • Participants will be instructed on how to perform blood ketone testing.

741 • Participants will be given guidelines for treatment of elevated blood ketones.

742 **6.2 Safety Measures**743 **6.2.1 CGM Calibration**

744 Throughout the study, participants will be instructed to calibrate the study CGM in accordance
745 with manufacturer labelling.

746 **6.2.2 System Failure**

747 If the CGM signal becomes unavailable for more than 20 minutes consecutively, Control-IQ or
748 closed loop will not operate to automatically adjust insulin. If the CGM is not connected, the
749 system will revert to usual function of the pump and deliver insulin with the insulin dosing
750 parameters programmed in the system for that individual. Resumption of Closed-Loop will
751 occur automatically once CGM signal is available again.

752 If the study system is unable to activate Control-IQ for any reason, the pump will automatically
753 revert to preprogrammed basal insulin delivery without any need for instruction from the user.

754 If the t:slim X2 detects a system error that does not allow the pump to operate, the Malfunction
755 Alarm will display and the participant will be instructed to contact Tandem Technical Support
756 via the study team.

757 **6.2.3 Hypoglycemia Threshold Alert and Safety Protocol**

758 During the course of the study, participants will be permitted to change the CGM low glucose
759 threshold alert setting on their device or mobile app, but will be instructed to choose a value no
760 less than 60 mg/dL.

761 The t:slim X2 with Control-IQ system will issue a predictive hypoglycemia alert (Control-IQ
762 Low Alert) when the system predicts BG <70 mg/dL within the next 15 minutes (<80 mg/dL
763 when exercise mode is activated).

764 If the participant receives a Control-IQ Low Alert, a message appears on the UI that is
765 accompanied by vibration followed by vibrations and/or sound if not acknowledged by the user
766 in 5 minutes. This alert remains on the screen until acknowledged by the user. The user is
767 prompted to test blood sugar and treat with carbs.

768 If a participant's CGM reading is <80 mg/dL, the Glycemic Treatment Guidelines will be
769 followed.

770 **6.2.4 Hyperglycemia Threshold Alert and Safety Protocol**

771 During the course of the study, participants will be permitted to change the CGM high glucose
772 threshold alert setting on their device or mobile app, but will be instructed to choose a value no
773 greater than 300 mg/dL.

774 The t:slim X2 with Control-IQ system will issue a predictive hyperglycemia alert (Control-IQ
775 High Alert) when the system has increased insulin delivery, but detects a CGM value above 200
776 mg/dL and does not predict the value will decrease in the next 30 minutes.

777 If the participant receives a Control-IQ High Alert, a message appears on the UI that is
778 accompanied by vibration followed by vibrations and/or sound if not acknowledged by the user
779 in 5 minutes. This alert remains on the screen until acknowledged by the user. The user is
780 prompted to check the site for occlusion and test blood glucose.

781 If a participant's CGM reading is >300 mg/dL for over 2 hours or ≥ 400 mg/dL at any point, the
782 Glycemic Treatment Guidelines will be followed.

783

Chapter 7: Point-of-Care Testing

784 **7.1 Point-of-Care Samples**

785 1. HbA1c:

786 • Performed locally at the Screening visit or a lab result that was completed within 2 weeks
787 prior to the Screening visit.

788 2. Urine Pregnancy:

789 • Performed locally for females of child-bearing potential at the Screening visit and prior to the
790 start of the Ski Admission.

791 **Chapter 8: Adverse Events, Device Issues, and Stopping Rules**

792 **8.1 Adverse Events**

793 **8.1.1 Definitions**

794 Adverse Event (AE): Any untoward medical occurrence in a study participant, irrespective of the
795 relationship between the adverse event and the device(s) under investigation (see section 8.1.2
796 for reportable adverse events for this protocol).

797 Serious Adverse Event (SAE): Any untoward medical occurrence that:

- 798 • Results in death.
- 799 • Is life-threatening; (a non-life-threatening event which, had it been more severe, might have
800 become life-threatening, is not necessarily considered a serious adverse event).
- 801 • Requires inpatient hospitalization or prolongation of existing hospitalization.
- 802 • Results in persistent or significant disability/incapacity or substantial disruption of the ability
803 to conduct normal life functions (sight threatening).
- 804 • Is a congenital anomaly or birth defect.
- 805 • Is considered a significant medical event by the investigator based on medical judgment (e.g.,
806 may jeopardize the participant or may require medical/surgical intervention to prevent one of
807 the outcomes listed above).

808 Unanticipated Adverse Device Effect (UADE): Any serious adverse effect on health or safety or
809 any life-threatening problem or death caused by, or associated with, a device, if that effect,
810 problem, or death was not previously identified in nature, severity, or degree of incidence in the
811 investigational plan or application (including a supplementary plan or application), or any other
812 unanticipated serious problem associated with a device that relates to the rights, safety, or
813 welfare of participants (21 CFR 812.3(s)).

814 Adverse Device Effect (ADE): Any untoward medical occurrence in a study participant which
815 the device may have caused or to which the device may have contributed.

816 Device Complaints and Malfunctions: A device complication or complaint is something that
817 happens to a device or related to device performance, whereas an adverse event happens to a
818 participant. A device complaint may occur independently from an AE, or along with an AE.
819 An AE may occur without a device complaint or there may be an AE related to a device
820 complaint. A device malfunction is any failure of a device to meet its performance specifications
821 or otherwise perform as intended. Performance specifications include all claims made in the
822 labeling for the device. The intended performance of a device refers to the intended use for
823 which the device is labeled or marketed. (21 CFR 803.3). Note: for reporting purposes, sites
824 will not be asked to distinguish between device complaints and malfunctions.

825 **8.1.2 Reportable Adverse Events**

826 For this protocol, a reportable adverse event includes any untoward medical occurrence that
827 meets one of the following criteria:

828 1. A serious adverse event
829 2. An Adverse Device Effect as defined in section 8.1.1, unless excluded from reporting in
830 section 8.
831 3. An Adverse Event occurring in association with a study procedure
832 4. Hypoglycemia meeting the definition of severe hypoglycemia as defined below
833 5. Diabetic ketoacidosis (DKA) as defined below or in the absence of DKA, a hyperglycemic or
834 ketosis event meeting the criteria defined below

835 Hypoglycemia and hyperglycemia not meeting the criteria below will not be recorded as adverse
836 events unless associated with an Adverse Device Effect. Skin reactions from sensor placement
837 are only reportable if severe and/or required treatment.

838 Pregnancy occurring during the study will not be considered an adverse event.

839 **8.1.2.1 Hypoglycemic Events**

840 Hypoglycemia not associated with an Adverse Device Effect is only reportable as an adverse
841 event when the following definition for severe hypoglycemia is met: the event required
842 assistance of another person due to altered consciousness, and required another person to actively
843 administer carbohydrate, glucagon, or other resuscitative actions. This means that the participant
844 was impaired cognitively to the point that he/she was unable to treat himself/herself, was unable
845 to verbalize his/ her needs, was incoherent, disoriented, and/or combative, or experienced seizure
846 or coma. These episodes may be associated with sufficient neuroglycopenia to induce seizure or
847 coma. If plasma glucose measurements are not available during such an event, neurological
848 recovery attributable to the restoration of plasma glucose to normal is considered sufficient
849 evidence that the event was induced by a low plasma glucose concentration.

850 **8.1.2.2 Hyperglycemic Events/Diabetic Ketoacidosis**

851 Hyperglycemia not associated with an Adverse Device Effect is only reportable as an adverse
852 event when one of the following four criteria is met:

- 853 • the event involved DKA, as defined by the Diabetes Control and Complications Trial
854 (DCCT) and described below
- 855 • evaluation or treatment was obtained at a health care provider facility for an acute event
856 involving hyperglycemia or ketosis
- 857 • blood ketone level ≥ 1.5 mmol/L and communication occurred with a health care provider at
858 the time of the event
- 859 • blood ketone level ≥ 3.0 mmol/L, even if there was no communication with a health care
860 provider

861 Hyperglycemic events are classified as DKA if the following are present:

862 • Symptoms such as polyuria, polydipsia, nausea, or vomiting;
863 • Serum ketones ≥ 1.5 mmol/L or large/moderate urine ketones;
864 • Either arterial blood pH < 7.30 or venous pH < 7.24 or serum bicarbonate < 15 ; and
865 • Treatment provided in a health care facility

866 All reportable Adverse Events—whether volunteered by the participant, discovered by study
867 personnel during questioning, or detected through physical examination, laboratory test, or other
868 means—will be reported on an adverse event form online. Each adverse event form is reviewed
869 by the Medical Monitor to verify the coding and the reporting that is required.

870 **8.1.3 Relationship of Adverse Event to Study Device**

871 The study investigator will assess the relationship of any adverse event to be related, possibly
872 related, or unrelated by determining if there is a reasonable possibility that the adverse event may
873 have been caused by the study device.

874 **8.1.4 Intensity of Adverse Event**

875 The intensity of an adverse event will be rated on a three point scale: (1) mild, (2) moderate, or
876 (3) severe. It is emphasized that the term severe is a measure of intensity: thus a severe adverse
877 event is not necessarily serious. For example, itching for several days may be rated as severe,
878 but may not be clinically serious.

879 • MILD: Usually transient, requires no special treatment, and does not interfere with the
880 participant's daily activities.

881 • MODERATE: Usually causes a low level of inconvenience or concern to the participant and
882 may interfere with daily activities, but is usually ameliorated by simple therapeutic measures.

883 • SEVERE: Interrupts a participant's usual daily activities and generally requires systemic
884 drug therapy or other treatment.

885 **8.1.5 Coding of Adverse Events**

886 Adverse events will be coded using the MedDRA dictionary. The Medical Monitor will review
887 the investigator's assessment of causality and may agree or disagree. Both the investigator's and
888 Medical Monitor's assessments will be recorded. The Medical Monitor will have the final say in
889 determining the causality.

890 Adverse events that continue after the participant's discontinuation or completion of the study
891 will be followed until their medical outcome is determined or until no further change in the
892 condition is expected.

893 **8.1.6 Outcome of Adverse Event**

894 The outcome of each reportable adverse event will be classified by the investigator as follows:

895 • RECOVERED/RESOLVED – The participant recovered from the AE/SAE without sequelae.
896 Record the AE/SAE stop date.

897 • RECOVERED/RESOLVED WITH SEQUELAE – The event persisted and had stabilized
898 without change in the event anticipated. Record the AE/SAE stop date.

899 • FATAL – A fatal outcome is defined as the SAE that resulted in death. Only the event that
900 was the cause of death should be reported as fatal. AEs/SAEs that were ongoing at the time
901 of death; however, were not the cause of death, will be recorded as “resolved” at the time of
902 death.

903 • NOT RECOVERED/NOT RESOLVED (ONGOING) – An ongoing AE/SAE is defined as
904 the event was ongoing with an undetermined outcome.

905 ◆ An ongoing outcome will require follow-up by the site in order to determine the final
906 outcome of the AE/SAE.

907 ◆ The outcome of an ongoing event at the time of death that was not the cause of death,
908 will be updated and recorded as “resolved” with the date of death recorded as the stop
909 date.

910 • UNKNOWN – An unknown outcome is defined as an inability to access the participant or
911 the participant’s records to determine the outcome (for example, a participant that was lost to
912 follow-up).

913 All clinically significant abnormalities of clinical laboratory measurements or adverse events
914 occurring during the study and continuing at study termination should be followed by the
915 participant’s physician and evaluated with additional tests (if necessary) until diagnosis of the
916 underlying cause, or resolution. Follow-up information should be recorded on source
917 documents.

918 If any reported adverse events are present when a participant completes the study, or if a
919 participant is withdrawn from the study due to an adverse event, the participant will be contacted
920 for re-evaluation within 2 weeks. If the adverse event has not resolved, additional follow-up will
921 be performed as appropriate. Every effort should be made by the Investigator or delegate to
922 contact the participant until the adverse event has resolved or stabilized.

923 **8.2 Reportable Device Issues**

924 All UADEs, ADEs, device complaints, and device malfunctions will be reported irrespective of
925 whether an adverse event occurred, except in the following circumstances.

926 The following device issues are anticipated and will not be reported but will be reported as an
927 Adverse Event if the criteria for AE reporting described above are met:

928 • Component disconnections

929 • CGM sensors lasting fewer than the number of days expected per CGM labeling

930 • CGM tape adherence issues

931 • Pump infusion set occlusion not leading to ketosis

932 • Battery lifespan deficiency due to inadequate charging or extensive wireless communication

933 • Intermittent device component disconnections/communication failures not leading to system
934 replacement

935 • Device issues clearly addressed in the user guide manual that do not require additional
936 troubleshooting

937 • Skin reactions from CGM sensor placement or pump infusion set placement that do not meet
938 criteria for AE reporting

939 **8.3 Pregnancy Reporting**

940 If pregnancy occurs, the participant will be discontinued from the study. The occurrence of
941 pregnancy will be reported on an AE Form.

942 **8.4 Timing of Event Reporting**

943 SAEs must be reported to the IRB per IRB reporting guidelines for this protocol.

944 Other reportable adverse events, device malfunctions (with or without an adverse event), and
945 device complaints should be reported promptly by completion of an electronic case report form,
946 but there is no formal required reporting period.

947 Upon knowledge of an UADE, the investigator will investigate the UADE and if indicated,
948 report the results of the investigation to the IRB, and the FDA within ten working days of the
949 investigator becoming aware of the UADE per 21CFR 812.46(b) (2). The Medical Monitor must
950 determine if the UADE presents an unreasonable risk to participants. If so, the Medical Monitor
951 must ensure that all investigations, or parts of investigations presenting that risk, are terminated
952 as soon as possible but no later than 5 working days after the Medical Monitor makes this
953 determination and no later than 15 working days after first receipt notice of the UADE.

954 In the case of a device system component malfunction (e.g. pump, CGM, control algorithm),
955 information will be forwarded to the responsible company by the site personnel, to be handled
956 by its complaint management system.

957 **8.5 Stopping Criteria**

958 **8.5.1 Participant Discontinuation of Study Device**

959 Rules for discontinuing study device use are described below.

960 • The investigator believes it is unsafe for the participant to continue on the intervention. This
961 could be due to the development of a new medical condition or worsening of an existing
962 condition; or participant behavior contrary to the indications for use of the device that
963 imposes on the participant's safety

964 • The participant requests that the treatment be stopped

965 • Participant pregnancy

966 • One episode of DKA

967 • One severe hypoglycemia event as defined in section 8.1.2.1

968 If pregnancy occurs, the participant will be discontinued from the study entirely. Otherwise, even
969 if the study device system is discontinued, the participant will be encouraged to remain in the
970 study through the final study visit.

971 **8.5.2 Criteria for Suspending or Stopping Overall Study**

972 In the case of a system malfunction resulting in a severe hypoglycemia or severe hyperglycemia
973 event (as defined in section 8.1.2.2), use of the study device system will be suspended while the
974 problem is diagnosed.

975 In addition, study activities could be similarly suspended if the manufacturer of any constituent
976 study device requires stoppage of device use for safety reasons (e.g. product recall). The
977 affected study activities may resume if the underlying problem can be corrected by a protocol or
978 system modification that will not invalidate the results obtained prior to suspension.

979 The study medical monitor will be informed of all serious adverse events and any unanticipated
980 adverse device events that occur during the study and will review compiled safety data at
981 periodic intervals. The medical monitor may request suspension of study activities or stoppage
982 of the study if deemed necessary based on the totality of safety data available.

983 **8.6 Risks**

984 The potential risks associated with use of the study device are described in section 1.3.

985 Additional risks are minor and/or infrequent and include:

986 • Pain, bruising, redness, or infection from blood draws
987 • Loss of confidentiality

988 **Chapter 9: Miscellaneous Considerations**

989 **9.1 Drugs Used as Part of the Protocol**

990 Participants will use either lispro or aspart insulin prescribed by their personal physician.

991 **9.2 Prohibited Medications, Treatments, and Procedures**

992 Participants using glulisine at the time of enrollment will be asked to contact their personal
993 physician to change their prescribed personal insulin to lispro or aspart for the duration of the
994 trial.

995 Treatment with any non-insulin glucose-lowering agent (including GLP-1 agonists, Symlin,
996 DPP-4 inhibitors, SGLT-2 inhibitors, biguanides, sulfonylureas and naturaceuticals) will be
997 reviewed by the study team. Use of these agents must be approved by the investigator prior to
998 initiation of study equipment.

999 The investigational study devices (t:slim X2 insulin pump, study CGM systems) must be
1000 removed before Magnetic Resonance Imaging (MRI), Computed Tomography (CT) or diathermy
1001 treatment. Participants may continue in the trial after temporarily discontinuing use if requiring
1002 one of the treatments above.

1003 **9.3 Participant Compensation**

1004 Participants will not receive compensation or reimbursement for his/her participation in this
1005 study.

1006 **9.4 Participant Withdrawal**

1007 Participation in the study is voluntary, and a participant may withdraw at any time.
1008 For participants who withdraw, their data will be used up until the time of withdrawal.

1009 **9.5 Confidentiality**

1010 For security and confidentiality purposes, participants will be assigned an identifier that will
1011 be used instead of their name. De-identified participant information may also be provided to
1012 Tandem for system evaluation purposes.

1013 **Chapter 10: Statistical Consideration**

1014 **10.1 Statistical and Analytical Plans**

1015 The approach to sample size and statistical analyses are summarized below. A detailed statistical
1016 analysis plan will be written and finalized prior to the first tabulation of data by treatment group
1017 (ie, for DSMB review). The analysis plan synopsis in this chapter contains the framework of the
1018 anticipated final analysis plan.

1019 **10.2 Statistical Hypotheses**

1020 The hypotheses for the primary outcome are:

- 1021 a. *Null Hypothesis*: the use of MyTDI results in a decreased percentage of the time spent
1022 between 70-180mg/dL during home use
- 1023 b. *Alternative Hypothesis* : the use of MyTDI does not results in a decreased percentage of
1024 the time spent between 70-180mg/dL during home use

1025 All outcomes will be analyzed using repeated measure ANOVA between baseline and the
1026 studied period, using within-between factors.

1027 We will compute all outcome for baseline, camp, and the final home segment. Outcomes will be
1028 further refined to focus on daytime (7am-11pm), nighttime (11pm-7am), and for the Ski
1029 Admission, ski time (9am-noon & 1:30pm-4:30)

1030 **10.3 Sample Size**

1031 We set the study to detect an effect size of 0.25 using repeated measure ANOVA and a within-
1032 between comparison (baseline – home, grouped by treatment), assuming 0.75 correlation
1033 between measurements. With N=20 we expect to reach 85% power, allowing for up to 2
1034 participants (10%) to fail to complete the study.

1035 **10.4 Outcome Measures**

1036 **10.4.1 Primary Efficacy Endpoint**

1037 The primary outcome for this study is the percent of time spent between 70mg/dL and 180mg/dL
1038 as computed by the number of CGM values falling in this interval divided by the total number of
1039 available CGM values. CGM gaps inferior to 3 hours will be linearly interpolated

1040 **10.4.2 Secondary Efficacy Endpoints**

1041 Additional CGM outcomes will include:

- 1042 • Percent CGM below 50mg/dL
- 1043 • Percent CGM below 54mg/dL
- 1044 • Percent below 60mg/dL
- 1045 • Percent CGM below 70mg/dL

1046 • Percent CGM above 180mg/dL
1047 • Percent CGM above 250mg/dL
1048 • Percent CGM above 300mg/dL:
1049 • Average CGM
1050 • CGM coefficient of variation
1051 • CGM based LBGI & HBGI
1052 Furthermore, we will compute
1053 • Total amount of insulin used
1054 • Number of Hypoglycemic episodes as defined by contiguous CGM below 70mg/dL
1055 • Number of rescue CHO
1056 • Total amount of rescues CHO

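### Section 10.2 sets out to show that MyTDI does not lower time in range but gives no margin, while the test and the 85% power are for detecting a difference

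*Combined protocol and SAP*

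**What the plan says.** Section 10.2 gives two hypotheses for the primary outcome, percent time in range (TIR) during home use. The null is that "the use of MyTDI results in a decreased percentage of the time spent" in range. The alternative is that "the use of MyTDI does not results in a decreased percentage of" that time. The boundary between them is therefore a difference of zero, and the burden is to rule out a decrease.

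The same section names one analysis: "All outcomes will be analyzed using repeated measure ANOVA between baseline and the" studied period, with within-between factors. Section 10.3 states: "We set the study to detect an effect size of 0.25" for the "between comparison (baseline – home, grouped by treatment") contrast, with a correlation of 0.75 between measurements. It continues: "With N=20 we expect to reach 85% power, allowing for up to 2" participants to be lost.

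No non-inferiority margin, confidence-interval criterion, alpha or sidedness appears in the documents. Section 10.1 says a detailed "analysis plan will be written and finalized prior to the first tabulation of data by treatment group", and describes chapter 10 as the framework for that plan.

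**The concern.** The hypothesis and the test do not match. The ANOVA tests whether the groups differ in their change from baseline. The written alternative is that MyTDI is no worse. With the boundary at zero and no margin, the only valid way to reject the written null is a significant result in favour of MyTDI, which is superiority. A significant result against MyTDI does not reject it, and neither does a non-significant one.

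The rationale in section 1.2 is that simple formulas based on total daily insulin could replace complicated home settings, so near-equality of the two groups is a plausible outcome. In that case the plan has almost no chance of supporting its stated alternative, and it does not say how a non-significant F test will be interpreted. The risk is that such a result from 20 adolescents is reported as showing that MyTDI does not worsen control, with the 85% cited in support.

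**Working it through.** **Inputs from the plan (10.2, 10.3):** effect size 0.25; correlation 0.75; two groups, 1:1; two measurements (baseline, home); N = 20, with up to 2 losses.

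**Inferred:** 0.25 is Cohen's f and alpha is 0.05 for the F test, because these reproduce the stated power. SD means the between-participant SD of TIR in one period, taken as equal in both periods. Its value is not given.

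**Step 1. Reproduce the 85%.** For the within-between interaction, λ = f² × N × 2 / (1 − ρ).
- N = 20: λ = 0.0625 × 20 × 2 / 0.25 = 10.0; F on 1 and 18 df at 0.05 gives power 84.8%.
- N = 18: λ = 9.0; F on 1 and 16 df gives 80.4%.
- At N = 20, alpha 0.10 gives 91.9%, alpha 0.025 gives 75.7%, and three measurements give 92.4%. Of these variants, only the two-measurement F test at 0.05 matches.

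**Step 2. Translate the effect.** With two groups and two times, the interaction test is a t test on change scores.
- Difference in change = 4f × SD = 4 × 0.25 = 1.0 SD.
- SD of change = √(2 × (1 − 0.75)) = 0.707 SD.
- Standard error = 0.707 × √(2/10) = 0.316 SD (10+10), or 0.707 × √(2/9) = 0.333 SD (9+9).
- Check: (1.0 / 0.316)² = 10, which equals λ.
- 95% CI half-width = 2.101 × 0.316 = 0.66 SD (10+10), or 2.120 × 0.333 = 0.71 SD (9+9).

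**Step 3. Chance of rejecting the written null.** This needs a significant result favouring MyTDI. At true equality the probability is 2.5%. At a true gain of 1.0 SD it is 84.8% with 20 completers.

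**Step 4. If a non-significant F were read as no decrease.** Probability of non-significance, from the noncentral t:

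| True loss | 20 completers | 18 (9+9) | 18 (10+8) |
|---|---|---|---|
| 0.5 SD | 68% | 71% | 71% |
| 0.75 SD | 39% | 44% | 44% |
| 1.0 SD | 15% | 20% | 20% |

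The loss missed half the time is 0.655 SD with 20 completers and 0.695 SD with 9+9. A simulation of 200,000 runs at N = 20 agrees: 0.0248 for Step 3 at equality, and 0.678, 0.387 and 0.152 for the three losses.

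**Step 5. What a margin rule could deliver.** Power at true equality to place the lower confidence limit above minus the margin:

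| Margin | One-sided 2.5%: 20 (18) | One-sided 5%: 20 (18) |
|---|---|---|
| 0.5 SD | 32% (29%) | 45% (42%) |
| 0.75 SD | 61% (56%) | 74% (69%) |
| 1.0 SD | 85% (80%) | 92% (89%) |

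At one-sided 2.5%, 85% power needs a margin of 1.00 SD with 20 completers or 1.06 SD with 18. A margin of 0.5 SD would need about 36 per arm (normal approximation).

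**Step 6. Scale in TIR points (assumption).** For an assumed SD of 10 to 15 points, the half-width is 6.6 to 10.0 points with 20 completers and 7.1 to 10.6 with 18.

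**The case against.** Chapter 10 is only a synopsis, and the SAP could supply alpha, sidedness and a margin. That is true, and it is why the point can be settled in time. But the chapter is declared to be the SAP's framework, and N is already fixed on a difference test.

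The plan never says a non-significant F will be taken as no decrease, so the miss rates in Step 4 describe an inference it has not made. This stands, and those figures are conditional. The plan does, however, leave that result without any stated interpretation. The 2.5% is simply half of a two-sided 0.05, as in any such test with a zero boundary; its relevance is that the 85% beside it does not apply at equality.

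The null and alternative labels may have been transposed. If so, a test for a difference fits better and the repair is largely editorial. The text does not say so, and a non-significant result would still not establish the absence of a decrease.

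This is a small single-site trial whose specific aims are safety and feasibility, so a formal margin may be more than it needs. That is an argument for restating the hypothesis, not for leaving it. The Protocol Summary also describes a randomized assessment of safety and efficacy, and the plan itself states hypotheses and power.

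Two neighbouring inconsistencies do not alter the result. The Protocol Summary defines the primary outcome over about 2 weeks, whereas 10.2 and 10.3 name the home segment. Section 2.1 expects all 20 participants to complete, whereas 10.3 allows 2 losses.

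**Conclusion.** The concern holds, with high confidence, and should be corrected before the SAP is finalized. The stated test can support the stated alternative only if MyTDI is significantly better. The 85% is power for a 1.0 SD difference with all 20 completing, and about 80% after the 2 allowed losses. It is not power to show no decrease when the settings perform alike; that probability is 2.5%. Under a margin rule at one-sided 2.5%, the same 85% applies only at a margin of about 1.0 SD of TIR. These figures rest on the plan's correlation of 0.75, on reading 0.25 as Cohen's f, and on an inferred alpha of 0.05. Results in percentage points also depend on an SD that the plan does not give.

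**What to change.** **Section 10.2 and the SAP.** Make the between-group difference in change in home-segment TIR, in percentage points with its 95% CI, the primary result. State alpha and sidedness. Then choose one:

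1. Keep the present hypothesis. Conclude no decrease only if the lower confidence limit lies above minus a margin in TIR points, justified clinically and fixed before any by-group tabulation.
2. State the tested null as no difference, which is what 10.3 powers.

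Under either option, say that a non-significant F test will not be read as showing no decrease.

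**Section 10.3.** State that 85% is power to detect a 1.0 SD difference with 20 completers, and about 80% with 18. State also that, at true equality and one-sided 2.5%, 85% power for a no-decrease conclusion needs a margin of about 1.0 SD (1.06 SD with 18). Give the assumed SD of TIR.

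**Cost.** Wording only, with no added participants, procedures or data. The trial's stated capability becomes less favourable. Option 1 with a margin well below 1.0 SD leaves the trial underpowered at its present size, and the margin should not be chosen to fit N. Option 2 changes the question the investigators wrote.
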